17.0 Risks to Subjects

17.1 List the reasonably foreseeable risks, discomforts, hazards, or inconveniences to the subjects related to the subjects' participation in the research. Include for the IRB's consideration a description of the probability, magnitude, duration, and reversibility of the risks. Consider physical, psychological, social, legal, privacy, and economic risks. Do not indicate "No risk" or "N/A." Instead, for studies with very low risk (e.g., anonymous online questionnaire on a mundane topic) indicate "The investigators are not aware of any risks from participation in this study." or "No more than risks than are found in everyday life." The example consent form presents a tabular method for risk information, which you can also use here. Common risk types include:

- *Physical (e.g., potential for pain, discomfort, infection)*
- *Psychological (e.g., potential for stress, discomfort, and/or embarrassment)*
- *Social (e.g., potential for discrimination or stigmatization and disruption of personal and family relationships)*
- *Legal (e.g., potential for disclosure of illegal activity, negligence)*
- *Privacy (e.g., potential for personal information being accessed, used, or disclosed without the subjects' knowledge or consent, breach of confidentiality/security)*
- *Economic (e.g., potential for individuals to lose access to economic services, employment, insurability)*

MRI data collection: The risks associated with collecting fMRI are the same as regular MRI. Movement or heating of metallic implants is a potential risk, therefore those with metallic pacemakers, fragments, or implants will be excluded from the study during screening. Some participants may experience claustrophobia in the scanner; any participant experiencing claustrophobia will be removed from the scanner immediately. fMRI scanners also produce loud noises while running which could be harmful to the subject. Participants will be required to wear earplugs and other ear protection during scans to minimize the noise generated by the scanner.

The Siemens 3 T scanner has been approved by the FDA. However, there may be additional risks associated with scanning at 3.0 T compared to the conventional clinical scanners in the 1.5-2.0 T range. These include:

1. Effect of the static field. There is no conclusive evidence for irreversible or hazardous bioeffects to acute, short-term exposures of humans up to 2.0 T (Shellock and Kanal, 1996). Studies have indicated some side-effects at 4.0 T, namely unusual sensations including nausea, vertigo, and metallic taste (Schenck, 1991). However, there is no evidence that this is either irreversible or harmful. If subjects experience unusual sensations, they will be withdrawn.
2. Effect of the gradient field. MRI operates by rapidly changing small additional fields, called gradients. This will induce small electrical currents in any conductor, and thus could theoretically induce mild peripheral nerve stimulation. However, this is not substantially different at higher magnetic fields since the gradients are separate from the main magnet. There is no evidence that the effect of the gradients is any different at 3 T than at 1.5 T. However, if subjects experience peripheral nerve stimulation, e.g. tingling or twitching, they will be withdrawn.
3. Effect of the RF electromagnetic field. The higher magnetic field strength requires that higher RF frequency pulses are used to excite the protons in the subject's brain. The limits of RF energy that can be safely given to humans has been clearly defined by the FDA: a). The exposure to RF energy below the level of concern is an SAR of 0.4 W/kg or less averaged over the body, and 8.0 W/kg or less spatial peak in any 1 g of tissue, and 3.2 W/kg or less average over the head; or b). The exposure to RF energy that is sufficient to produce a core temperature increase of 1 degree C and localized heating to no greater extent than 38 degrees C in the head, 39 degrees C in the trunk, and 40 degrees C in the extremities, except for patients with impaired systemic blood flow and/or perspiration. We will adhere to the recommendations for the head, which is also monitored by a Siemens built-in monitor.
4. Acoustic Noise Levels. Rapid changes in the currents in the gradient coils of the MRI scanner produce significant levels of acoustic noise. The levels of noise range approximately between 65 and 95 dB, but could have higher peaks. Communications with subjects takes place with the standard intercom system provided by the scanner manufacturer.. Foam ear plugs with a Noise Reduction Rating of at least 30 dB will be provided.

Subjects may experience discomfort, such as anxiety during the MRI scanning. Subject comfort will be reassessed and subjects will be allowed to discontinue any session at any time.

The subject may communicate with the experimenter at any time: 1) before, in between, or after a scan via an intercom device between the scanner and control room, and 2) during a scan via a pneumatic squeeze bulb located in the scanner that triggers an alarm in the control room. Subjects who report discomfort and wish to discontinue their participation will be immediately withdrawn from the scanner. Subjects who are withdrawn from the study will be compensated for their participation to that point.

IV Catheter Blood Draws:

All catheter placements and draws will be performed by a trained and skilled medical technologist, phlebotomist, or nurse in the appropriate laboratory setting with proper antiseptic technique. However, there are still some risks of this procedure. Some pain or discomfort may be experienced when the catheter is inserted in the vein, but this should persist for only a short time. During the blood draws, there may be pain and/or bruising at the site where the IV catheter is inserted. In rare cases infection or blood clot may occur at the IV catheter site. These are the same risks associated with IV catheter placement in any medical setting. Inclusion criteria for this study include non-pregnant adults who weigh at least 110 lbs. Blood collection during draws will total ~189 ml over a 3-week period (~63 ml per week), well below the minimal risk cutoff of 550 ml in an 8-week period. In this study, blood collection occurs 1 time per week. Thus, this study fits the defined criteria for imposing minimal risk.

Beverage and food stimuli: All components of the beverage and food stimuli are readily available outside the laboratory (grocery stores, etc.) and are likely already consumed by the participants. There are no known risks associated with these stimuli.

Indirect Calorimetry. There are no known risks associated with the noninvasive indirect calorimetry methods. These non-invasive procedures are simple and painless, and normal clothes can be worn during the procedures. For the metabolic chamber procedure, subjects will be lying back on a bed in a small room with plexiglass windows. The subjects will then be asked to relax and breathe normally during the entirety of the testing. During the testing, the study staff will be able to see and hear participants so should they, at any time during the testing, become uncomfortable in the chamber, they may choose to stop the procedure.

Eating Behavior Questionnaires

There is a small potential psychological risk associated with some questions that refer to frequency of induced vomiting, distress associated with overeating. The questionnaires included in this study are frequently used and validated questionnaires in nutrition research, including research in eating disorders and disordered eating. They are important in assessing several unique aspects of eating behavior that could influence our study outcomes.

Loss of Confidentiality

There is a small risk of loss of confidentiality of data during the study. Please see sections 9.0, 17.2, and 19.0 for more details about these risks and also steps taken to mitigate risk.

17.2 Indicate the measures you will use to minimize risks and monitor subjects for safety. (e.g., asking a subject at regular intervals to rate how they are feeling from 1 to 10, or to slowly crouch in order to check their balance.)

Indirect calorimetry: All indirect calorimetry measurements will be performed by trained personnel. Subjects who become uncomfortable over the course of the measurement can withdraw at any time.

MRI: In order to minimize noise from the MRI scanner that can be potentially harmful for the subject, all subjects will be required to wear ear protection while in the scanner. The subject may communicate with the experimenter at any time: 1) before, in between, or after a scan via an intercom device between the scanner and control room, and 2) during a scan via a pneumatic squeeze bulb located in the scanner that triggers an alarm in the control room. Subjects who report discomfort and wish to discontinue their participation will be immediately withdrawn from the scanner. Subjects who are withdrawn from the study will be compensated for their participation to that point.

Advanced MR/Operator Training: Required for those persons wishing to conduct research on the HNL MRIs. Training will consist of presentations, observation, and hands-on practice. Topics will include safety and emergency procedures, subject screening and preparation, scanner set-up and operation, and troubleshooting. Each person must also complete at least 4 hours of observation (to include 2 different studies) and at least 16 hours of supervised scanning (to include 4 different studies). Certification will be granted upon completion of the training and passing of a competency exam. Certified operators will conduct each scanning session.

IV Catheter Blood Draws: To reduce the risks associated with inserting an IV catheter and drawing blood from the catheter, only skilled medical technologists, nurses and/or other medical professionals will insert the IV catheters and draw the blood samples. In addition, a maximum of three attempts will be made to insert the catheter in the participants' arm during a given session.

Fingerstick Blood Sample

The risks associated with performing a fingerstick to collect a capillary blood sample are minimal. The likely risks involve pain and bleeding in the fingertip at the collection site. Rarely, an infection may occur at the puncture site. To minimize these risks, research team members will be trained on the proper technique for obtaining a capillary blood sample and care for the site after the sample is obtained.

Eating Behavior Questionnaires

There is a small potential psychological risk associated with some questions that refer to frequency of induced vomiting, distress associated with overeating. The questionnaires included in this study are frequently used and validated questionnaires in nutrition research, including research on eating disorders and disordered eating. They are important in assessing several unique aspects of eating behavior that could influence our study outcomes. To mitigate risk, participants will be not be required to answer these questions.

Loss of Confidentiality

There is a small risk of loss of confidentiality of data during the study. However, study personnel will make every effort to minimize this risk. Please see sections 9.0 and 19.0 for more detailed information about steps taken to mitigate risk. Briefly:

All study data will be collected and analyzed by trained research personnel.
Each participant will be assigned a coded designation and all study data to be used in the analysis will be de-identified using this coded designation. The de-identified data will not contain any biographical data that can be linked to study participants.
The “key” to the study code will be stored in a separate database which cannot be accessed without specific authorization.
Other screening documents will be stored on site in a locked cabinet that will only be accessible to authorized personnel.
Only personnel who are direct members of the research team will have access to personally identifiable information.
Data acquired during experiments will be collected and stored on a secure server managed by FBRI.

17.3 If applicable, indicate which procedures might have risks to the subjects that are currently unforeseeable. This will be rare, and usually applicable when testing a new drug or device or a new use of an existing drug or device:

There are no new devices or drugs used in this study.

17.4 If applicable, indicate which procedures might have risks to an embryo or fetus should the subject be or become pregnant:

None of the procedures used in this study have been known to cause risk to a fetus or embryo.

17.5 If applicable, describe risks to others who are not subjects (e.g., collection of sensitive health data that might affect sexual partners if disclosed, mandatory reporting of abuse, DNA testing that might affect family members or relationships):

N/A

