Participants will rate their hunger, thirst, and fullness on standard visual analog scales while fasted and after consumption of the beverage, along with perceptual ratings about the beverages consumed during the session.

IV Blood Draws

An IV catheter will be inserted into the participant's arm for venous blood draws throughout the session. This catheter will remain in the participant's arm for the duration of the session (~4 hours). A fasting baseline draw will be made, and then six additional blood draws after the participant consumes the conditioning beverage will be conducted throughout the remaining session. Two tubes of no more than 5 ml each will be collected at each blood draw (14 tubes total). This is approximately 126 ml of blood in total (~8-9 tablespoons). This is roughly equivalent to 1/4 the amount of blood given during a typical blood donation. All blood draws will occur while the participant is reclining on a bed inside a metabolic chamber (see Metabolic Chamber Indirect Calorimetry below). For the draws, the researcher performing the blood draws will reach their arms into the chamber via ports on the side of the chamber walls. Participants will be able to communicate with research personnel using a 2-way intercom system, and the walls of the metabolic chamber are clear plexiglass that allow researchers and participants to see each other throughout the measurement. IV blood draws occur concurrently with metabolic chamber measurements (see below). The IV catheter line will be flushed with normal saline between each blood draw to prevent coagulation in the catheter tubing. After the final blood draw, the catheter will be removed and the venipuncture site secured with sterile tape or bandage. Should the IV catheter placement fail or become unusable during the session, the catheter will be removed and participants will continue with the metabolic chamber indirect calorimetry portion of the session.

Metabolic Chamber Indirect Calorimetry

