14.0 Number of Subjects

14.1 Indicate the total number of subjects to be enrolled and how this number was determined (e.g., sample size calculation [show], number of available subjects in a finite pool, number of tests funding award would allow):

For the pilot study, we plan to consent 25 participants with the intent of having 20 complete the pilot study session.

For the full study, we plan to consent approximately 200 participants with the intent of having 70 participants complete Aim 1 and 70 participants complete Aim 2. These numbers were determined using power calculations based on other studies with similar designs conducted by our lab. We anticipate ~30% rate of either drop-out or exclusion after enrollment (e.g., unable to determine flavors equally liked and unfamiliar for the conditioning paradigm, hemoglobin A1C outside of the inclusion range, scheduling challenges, etc.).

14.2 If this is a multi-site study, indicate the number of subjects to be enrolled at this site and the total to be enrolled from all sites:

Single site

14.3 If applicable, indicate the number of potential subjects you expect to screen for enrollment, and the number of subjects you will need to complete the research procedures:

For the pilot study, we anticipate screening via the online screening process approximately 25 potential participants. We anticipate enrolling and screening approximately 20 participants during the Consent Session. We intend to have 20 participants complete the pilot study.

For the full study, we anticipate screening via the online screening process approximately 2000 potential participants. We anticipate enrolling and screening approximately 200 participants during the Consent Session. We intend to have 70 participants complete Aim 1 and 70 participants complete Aim 2. We anticipate that a majority of these participants will complete only 1 aim; however, it is possible and allowable for participants to complete both aims if they qualify for both (i.e., at least 6 flavors are rated as equally liked and equally unfamiliar in the Consent Session).

14.4 If the study has more than one procedure, indicate the total number of subjects to undergo each procedure separately:

Pilot Study (single session for each sweet mixture): 20 participants

Full-Study

Consent Session (flavor tasting/rating, anthropometrics, fingerstick sample for HbA1C): 200 participants

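### The ~189 ml behind the minimal-risk statement in 17.1 covers one aim, but one person may complete both, and that person's 8-week total is not stated

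*Combined protocol and SAP*

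**What the plan says.** Section 17.1 (IV Catheter Blood Draws) compares a three-week total with a cutoff of 550 ml in 8 weeks: "Blood collection during draws will total ~189 ml over a 3-week period (~63 ml per week), well below the minimal risk cutoff". It adds: "In this study, blood collection occurs 1 time per week". From this it concludes that the study as a whole is minimal risk, and 22.2 repeats that conclusion.

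Section 14.3 says that "it is possible and allowable for participants to complete both aims if they qualify for both", the condition being at least six flavors rated equally liked and equally unfamiliar. It expects most participants to complete only one aim. Section 15.4 sets a payment of $800 for both aims with a single consent session.

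Section 8.2 (Full Study, Overview) gives both aims the same design, so the second aim repeats the three catheter sessions. It caps each aim at 6 weeks. It sets no minimum time between aims, and I found none elsewhere, nor any cumulative blood limit per person.

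On volume per session, 8.2 (IV Blood Draws) says: "A fasting baseline draw will be made, and then six additional blood draws after the participant consumes the conditioning beverage". It continues: "Two tubes of no more than 5 ml each will be collected at each blood draw (14 tubes total". It then gives the volume: "This is approximately 126 ml of blood in total (~8-9 tablespoons".

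**The concern.** The comparison with 550 ml is the argument that 17.1 gives for calling the blood collection minimal risk. The figure compared should therefore be the largest that the protocol allows for one person. The figure used is for someone who takes part in one aim. A participant in both aims has twice as many sessions, and nothing in the documents keeps those sessions from falling inside one 8-week window. That participant is the one closest to the cutoff, and 17.1 does not assess that case.

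Settling the conflict between ~63 ml and ~126 ml per session would not repair this. Whichever volume is confirmed, the total for both aims would still be unstated.

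**Working it through.** **Inputs**
- Sessions per aim: 3 (11.1: 4 hours each, 12 hours total). Both aims: 6 (8.2, 14.3).
- Draws per session: 1 + 6 = 7. Tubes: 7 × 2 = 14. Tube maximum: 14 × 5 ml = 70 ml (8.2).
- Volume per session as printed: ~63 ml (17.1) and ~126 ml (8.2).
- Cutoff: 550 ml in 8 weeks, i.e. 56 days (17.1).

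**The plan's own figure.** 3 × 63 = 189 ml reproduces 17.1 exactly, as three sessions and so one aim. The figures in 8.2 do not give it: 3 × 70 = 210 ml and 3 × 126 = 378 ml.

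**Totals by session volume**

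| Volume per session | One aim (×3) | Share of 550 | Both aims (×6) | Share of 550 | Margin to 550 |
|---|---|---|---|---|---|
| 63 ml (17.1) | 189 ml | 34% | 378 ml | 69% | 172 ml under |
| 70 ml (8.2, tube maximum) | 210 ml | 38% | 420 ml | 76% | 130 ml under |
| 126 ml (8.2, printed) | 378 ml | 69% | 756 ml | 137% | 206 ml over |

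For one aim, no volume in the documents reaches the cutoff.

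**Can six draws fall within 8 weeks?** Take weekly draws within each aim, as 17.1 describes, and let g be the days from the last Aim 1 draw to the first Aim 2 draw. The six draws span 14 + g + 14 = 28 + g days. One possible schedule has draws on days 0, 7 and 14, a post-test about day 21, and draws on days 28, 35 and 42. There g = 14 and the span is 42 days. In whole weeks:

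| g (days) | Span (days) | Most draws in any 56 days | At 63 ml | At 70 ml | At 126 ml |
|---|---|---|---|---|---|
| 7 | 35 | 6 | 378 | 420 | 756 |
| 14 | 42 | 6 | 378 | 420 | 756 |
| 21 | 49 | 6 | 378 | 420 | 756 |
| 28 | 56 | 5 | 315 | 350 | 630 |
| 35 | 63 | 4 | 252 | 280 | 504 |
| 42 | 70 | 3 | 189 | 210 | 378 |

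All six draws stay in the window up to a gap of 21 days. At 42 days the 8-week total is back to that of one aim.

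**The case against.** The arithmetic in 17.1 is right for what it covers. It says three weeks, and at one session a week ~189 ml also holds for any three weeks of a participant in both aims. The gap is one of scope.

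A reader might infer that participants in both aims exceed the cutoff and that the minimal-risk statement fails. The documents do not support that. At 63 ml, or at the 70 ml tube maximum, the six-session total stays below 550 ml. Only ~126 ml per session takes it over. That figure appears in 8.2 beside a tube limit that allows at most 70 ml, and it is twice the figure in 17.1. It is restated there in tablespoons and as a fraction of a donation, so it cannot simply be ignored, but the excess depends on it.

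A reader might also infer that the aims run back to back, or that the eligibility criteria provide for taking part in both. The documents are silent on the interval, so the 42-day schedule is a possible case and not the stated plan. The permission is in 14.3 and 15.4; 12.2 does not mention it. Nor can the absence of safety endpoints be traced to the blood volume, because 4.2 gives no reason.

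Few people may be affected. Section 14.3 expects a majority to do one aim, and enrolment works with nobody doing both: 200 consented less ~30% is 140, or 70 per aim.

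These points limit the size of the problem. They do not remove it, because the protocol plans and pays for participation in both aims and 17.1 draws its conclusion for the whole study.

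**Conclusion.** The point holds as an omission in the risk statement. The ~189 ml in 17.1 describes one aim. For a participant in both aims, the 8-week total can be 378 ml on the volume in 17.1, twice the printed figure, or 420 ml at the tube maximum in 8.2. The share of the cutoff rises from 34% to 69% or 76%. On either volume the minimal-risk comparison survives with a smaller margin. On the ~126 ml in 8.2 it does not, at 756 ml (137%), and that result is conditional on a figure that the protocol contradicts.

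This assumes weekly draws within each aim and about 21 days or less between the last draw of one aim and the first draw of the other. With longer gaps fewer draws fall in the window. The number of participants in both aims is not given; 14.3 implies a minority.

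**What to change.** Reconcile 8.2, 14.3, 15.4 and 17.1 so that one volume per session and one account of participation in both aims run through the protocol. Then restate in 17.1 the maximum blood total per person for someone completing both aims, compare it with 550 ml in 8 weeks, and state the timing between aims that the comparison assumes. Which volume is correct, and whether any interval should apply, is for the sponsor and the investigator; neither is proposed here.

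The cost is wording in these sections and a less favourable printed figure. The statistical analysis is unaffected.
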